8.1 Subject Disposition

The following summary will be provided based on the Screened Analysis Set (see [Section 5.1](#)):

- Number and percentage of subjects who provided Informed Consent.
- Number and percentage of subjects screened.
- Number and percentage of subjects not assigned to treatment (screen failures) with reason for screen failure.
- Number and percentage of subjects enrolled, i.e., eligible to enter the study.
- Number and percentage of subjects eligible to enter the study but not treated.
- Number and percentage of subjects who received any dose of IP.

-
- Number and percentage of subjects who completed treatment per entry on the eCRF 'End of Treatment' ("Did the subject complete the treatment period?" Answer: "Yes").
 - Number and percentage of subjects who completed the study per entry on the eCRF 'Conclusion of Subject Participation' ("Did the subject complete the study?" Answer: "Yes").
 - Number and percentage of subjects with at least 12 months treatment period (i.e. subjects with reported Month 12 / EoT Visit in eCRF).
 - Number and percentage of subjects who completed the Follow-up Visit as required.
 - Number and percentage of subjects who did not completed the Follow-up Visit because they continued in the post-study access program or another prophylactic treatment.
 - Number and percentage of subjects who prematurely discontinued treatment during the Treatment Period with reason for treatment discontinuation (percentages based on the number who discontinued).
 - Number and percentage of subjects who discontinued the study during the Treatment Period with reason for study discontinuation (percentages based on the number who discontinued).
 - Number and percentage of subjects who discontinued the study during Follow-up Period with reason for study discontinuation (percentages based on the number who discontinued).
 - Number and percentage of subjects in the Screened Analysis Set.
 - Number and percentage of subjects in the Enrolled Analysis Set.
 - Number and percentage of subjects in the Safety Analysis Set.
 - Number and percentage of subjects in the PP Analysis Set.
 - Number and percentage of subjects in the PK Analysis Set.
 - Number and percentage of subjects in the PD Analysis Set.

Note:

Subjects may discontinue treatment but remain in the study until the Follow-up Visit. These subjects will be reported for treatment discontinuation, but not for study discontinuation. Other subjects may discontinue treatment and discontinue the study during the treatment period. These subjects will be reported for treatment and study discontinuation. Subjects who choose not to continue to receive CSL312 or another prophylactic treatment after this study may complete treatment and discontinue from the study during follow-up. These subjects will be reported for study discontinuation but not for treatment discontinuation. Subjects who choose to continue to receive CSL312 or another prophylactic treatment after this study will be reported as study completer if they completed treatment and not entered the Follow-up Period provided they answered the corresponding question in the eCRF ("Did the subject complete the study?") with "Yes".

Reasons for study and study treatment discontinuation will be presented in the order they are displayed in the eCRF.

The following by-subject listings will be provided:

- Disposition including date of informed consent, date of eligibility, date of first and last IP administration, EoT Visit date, Follow-up Visit date, reason for treatment discontinuation and/or study discontinuation.
- Assignment to analysis sets (included in Analysis Set: Screened Analysis Set [yes, no], Enrolled Analysis Set [yes, no], PP Analysis Set [yes, no], Safety Analysis Set [yes, no], PK Analysis Set [yes, no], PD Analysis Set [yes, no], reason(s) for exclusion from any analysis set).

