### Number of Subjects

The target sample size for this study is approximately 20 subjects to ensure that at least 15 subjects complete 12 months of treatment.

**Note:** Subjects are considered “enrolled” in the study when they, or their legally authorized representative, has agreed to participate in a clinical study after completing the informed consent process and Screening. Potential subjects who are screened to determine their eligibility but fail Screening or do not meet all eligibility criteria are not considered enrolled.

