## **7. SUBJECT WITHDRAWAL AND DISCONTINUATION OF INVESTIGATIONAL PRODUCT**

### **7.1. Discontinuation of Investigational Product**

Subjects may discontinue investigational product at any time at their own request, or at the discretion of the investigator or the sponsor for safety, behavioral, or administrative reasons.

Subjects who discontinue investigational product will remain in the study to complete follow-up activities or allow data collection as detailed in the Schedule of Activities ([Section 1.3](#)). Subjects discontinuing investigational product who decline further study procedures / visit participation will be withdrawn from the study (see [Section 7.2](#)).

Primary oversight during the conduct of the study will be the responsibility of the investigator. The investigator is responsible for evaluating the appropriateness of subjects to be enrolled in the study and for communicating any issues that may compromise subject safety with the sponsor to ensure appropriate action can be taken to protect subjects. Safety surveillance, medical safety assessment, and risk management will be conducted by the sponsor's Global Safety Committees as per Safety Processes at the sponsor. Additionally, an Independent Data Monitoring Committee (IDMC) will be established to monitor the efficacy and safety data generated during the study ([Section 10.1.8.1](#)). The IDMC will review accumulating data from the ongoing study. Based on these reviews, the IDMC will advise on the further conduct of the study.

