## **7.2. Subject Withdrawal from the Study**

Subjects may withdraw from the study at any time at their own request or may be withdrawn at any time at the discretion of the investigator or the sponsor for safety, behavioral, compliance, or administrative reasons (eg, AE, protocol deviation, subject noncompliance, or study termination).

The investigator may advise a subject to withdraw from the study if the subject's safety or wellbeing is compromised by further participation in the study. The interests of the subject must always prevail over the interests of the study.

At the time of subject withdrawal, if possible, the End of Treatment Visit assessments should be completed and documented (see Schedule of Activities in [Section 1.3](#)). If the subject is withdrawn from the study after receiving CSL312, every effort must be made to ensure that the relevant safety assessments are completed. The investigator may ask the subject to complete additional study assessments.

If a subject withdraws from the study, the sponsor may retain and continue to use any data collected before the subject's withdrawal of consent.

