This SAP complies with the International Council for Harmonisation (ICH) E9 'Statistical Principles for Clinical Trials' and E9(R1) 'Statistical Principles for Clinical Trials: Addendum on Estimands and Sensitivity Analysis in Clinical Trials', and is based upon the following study documents:

- Clinical Study Protocol Amendment 3, dated 9 January 2025
- electronic Case Report Form (eCRF), Version dated 30 Jan 2025

Population pharmacokinetic (PK) analyses are described within the modeling and simulation analysis plan (MSAP) and reported separately.

Mock tables, listings, and figures (TLF) shells are provided in a separate supporting document.

All decisions regarding the final analysis of the study results, as defined in this SAP, have been made before database lock (DBL) of the study data. Deviations from the planned analyses in this SAP will be detailed in the CSR.

3 Study Design

This is a multicenter, open-label, phase 3b pediatric study designed to investigate the safety, PK / pharmacodynamics (PD), and efficacy of subcutaneous (SC) administered CSL312 in the prophylactic treatment of hereditary angioedema (HAE) in children 2 to 11 years of age. The study schematic is shown in [Figure 1](#). The study will enroll a target sample size of approximately 20 subjects to ensure that at least 15 subjects complete 12 months of treatment.

[figure not shown]
The following subjects will be eligible to participate in this study if they meet all eligibility criteria:

- CSL312-naïve pediatric subjects with C1-esterase inhibitor (C1-INH) HAE type 1 or 2

CSL312 will be administered SC at a dose of 100 mg once monthly (Q1M; subjects 6 to 11 years of age) or every 2 months (Q2M; subjects 2 to 5 years of age) for at least 12 months.

The study will consist of a Screening Period, an open-label Treatment Period, and Follow-up Period. The Follow-up Visit takes place 3 months after last dose of CSL312. Subjects who complete the study have the option to continue treatment with CSL312 or another prophylactic treatment without a scheduled follow-up. Subjects who do not choose the post-study access program or another prophylactic treatment will complete the Follow-up Visit as mandated in this study.

Figure 1 Overall Study Schema

C1-INH = C1-esterase inhibitor; HAE = hereditary angioedema.

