3.4 Determination of the Sample Size

No formal sample size calculation is made, and the sample size is not based on formal statistical considerations. This study will enroll a prespecified number of subjects as agreed with health authorities. See [Section 5.2](#) for definition of "enrolled".

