7.4 Study Periods and Time Windows Relative to Treatment

The following definitions for the periods of efficacy and safety will be used to define the durations used in the denominator of the time-normalized endpoints and safety endpoints such as exposure and subject-years. The definitions of the time windows will be used in the efficacy analyses and the analysis of TEAEs.

Table 3 Overview of Study Periods and Time Windows

Study Period	Start Date	End Date	Duration
Screening Period	Informed Consent date	Day 1 Visit date - 1 if Informed Consent Date is before Day 1 Visit date. Informed Consent date if Informed Consent date is on Day 1 Visit date.	End Date - Start Date + 1 if Informed Consent Date is before Day 1 Visit date. 0 if Informed Consent date is on Day 1 Visit date.
Treatment Period/ Efficacy Evaluation Period	Day 1 Visit date or date of first IP if available	End of Treatment (EoT) Visit date or for premature discontinuations without the EoT Visit the last available visit or event date [whichever occurs later]. If the EoT Visit of a subject is delayed by more than the treatment time window relative to the last IP administration, EoT Visit date will be set to last IP administration + 30 days or + 60 days for Q1M or Q2M, respectively.	End Date - Start Date + 1
Follow-up Period if applicable	EoT Visit date + 1	Follow-up Visit or for premature discontinuations after the EoT Visit the last available visit or last event date [whichever occurs later]	End Date - Start Date + 1
Safety Evaluation Period	Date of first IP	Subjects who choose not to continue to receive CSL312 or another	End Date - Start Date + 1

Study Period	Start Date	End Date	Duration
		prophylactic treatment: Follow-up Visit or for premature discontinuations the last available visit or last event date [whichever occurs later]. Subjects who choose to continue to receive CSL312 or another prophylactic treatment: EoT Visit or for premature discontinuations without the EoT Visit the last available visit or last event date [whichever occurs later].	
Time Window	Start Date	End Date	Duration
Efficacy: Day 1 Until Day 31	Day 1 Visit date or date of first IP if available	Study day 31	End Date – Start Date + 1
Efficacy: First 6 Months	Day 1 Visit date or date of first IP if available	Month 6 (Day 181) Visit Date	End Date – Start Date + 1

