Efficacy: Second 6 Months	Month 6 (Day 181) Visit Date + 1 day	Month 12 (Day 361) EoT Visit Date. If the EoT Visit of a subject is delayed by more than the treatment time window relative to the last IP administration, EoT Visit date will be set to last IP administration + 30 days or + 60 days for Q1M or Q2M, respectively.	End Date – Start Date + 1
Safety: First 3 Months	Date of first IP	EoT date if subjects discontinued or date of first IP + 90 if subjects is ongoing	End Date – Start Date + 1
Safety: Second 3 Months	End Date of previous 3- Months' Time Window + 1	EoT date if subjects discontinued or start date + 90 if subjects is ongoing	End Date – Start Date + 1
Safety: Third 3 Months	End Date of previous 3- Months' Time Window + 1	EoT date if subjects discontinued or start date + 90 if subjects is ongoing	End Date – Start Date + 1

Time Window	Start Date	End Date	Duration
Safety: Fourth 3 Months	End Date of previous 3-Months' Time Window + 1	EoT date if subjects discontinued or start date + 90 if subjects is ongoing	End Date – Start Date + 1
Safety: Fifth 3 Months (if applicable)	End Date of previous 3-Months' Time Window + 1	EoT date if subjects discontinued or start date + 90 if subjects is ongoing	End Date – Start Date + 1
...			

Note:

The first day of the Treatment Period may occur on the same day as the Screening Visit for subjects meeting the eligibility criteria for the study. In this case, the duration of the Screening Period is 0.

The Follow-up Visit is mandatory in this study unless a subject chooses to continue to receive CSL312 (and meet the criteria to participate in a post-study access program) or another prophylactic treatment. For these subjects, the Follow-up Period is not applicable.

The length of the month in the 3-Months' Safety time windows is set to 30 days.

8 Study Population

Unless otherwise stated, all tables and listings in this section will be presented by dosing regimen (100 mg Q2M and 100 mg Q1M) and overall.

Subjects who turn 6 years of age during the study will remain on their dosing regimen from study start and will be analyzed for the age group at their date of consent.

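### SAP 8.1 counts a subject as having at least 12 months of treatment on the strength of a reported Month 12 / EoT Visit alone, so early withdrawals and off-drug attendees can be included

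*SAP*

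**What the plan says.** **The row.** SAP 8.1 lists among its disposition summaries: "Number and percentage of subjects with at least 12 months treatment period (i.e. subjects with reported Month 12 / EoT Visit in eCRF". The visit is the whole definition.

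**Completion in the protocol.** Protocol 4.5 sets two conditions for completing the study: 12 months of treatment, and the EoT Visit. Protocol 6.9 repeats both.

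**Subjects who stop early.** Protocol 7.2 says: "At the time of subject withdrawal, if possible, the End of Treatment Visit assessments should be completed and documented". Protocol 7.1 says: "Subjects who discontinue investigational product will remain in the study to complete follow-up activities or allow data collection".

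**The SAP's own period definition.** In SAP 7.4, Table 3 ends the Treatment Period at the EoT Visit date, or "for premature discontinuations without the EoT Visit the last available visit or event date". If the EoT Visit is late relative to the last dose, the end date is reset to the last dose plus 30 days (Q1M) or 60 days (Q2M). The 3-month safety windows in the same table end at "EoT date if subjects discontinued or date of first IP + 90 if subjects is ongoing".

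**The target.** Protocol 1.1 states: "The target sample size for this study is approximately 20 subjects to ensure that at least 15 subjects complete 12 months of treatment". SAP Section 3 repeats it. SAP 3.4 adds that "the sample size is not based on formal statistical considerations".

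**The concern.** The row's label describes a length of treatment, but its rule tests only whether a visit was recorded. A subject can have that visit without 12 months of treatment in two ways:

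1. The subject withdraws early and the EoT assessments are done at withdrawal, as Protocol 7.2 asks.
2. The subject stops the product, stays in the study under Protocol 7.1, and attends Month 12 off drug.

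This is the only disposition row that states a 12-month duration, so a reader of the study report would naturally set it beside the figure of 15. At stake is the accuracy of one descriptive count, and its agreement with Protocol 4.5 and with the SAP's own Table 3.

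**Working it through.** **1. The plan's own figure.** About 20 enrolled for at least 15 completers implies a loss of 1 − 15/20 = 25%, and 15 / (1 − 0.25) = 20. The 25% is back-calculated. Neither document states a dropout rate, so there is no derivation to reproduce.

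**2. Can an early discontinuer have an EoT Visit?** Table 3 gives a fallback end date only for premature discontinuations that lack the visit, so it allows for others that have it. The safety windows use an EoT date for discontinued subjects. Protocol 7.2 asks for the assessments at withdrawal. The three agree: it can happen.

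**3. Off-drug attendance against Table 3.** Take a Q1M subject last dosed on Day 181 who attends Month 12 on Day 361.
- Gap from last dose to visit: 361 − 181 = 180 days, so the Table 3 reset applies.
- Treatment Period end: 181 + 30 = Day 211. Duration: 211 − 1 + 1 = 211 days.
- SAP 8.1 row: counted as at least 12 months.

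The SAP thus gives two incompatible answers for the same subject.

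**4. Possible size of the miscount.** Suppose 20 subjects are treated, *w* withdraw early, and *e* of those have an EoT Visit recorded. The true count is 20 − *w*; the row reads 20 − *w* + *e*, with *e* between 0 and *w*. The documents give neither *w* nor *e*, so both are assumptions.

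| *w* | True count | Row can read | Smallest *e* for the row to reach 15 |
|---|---|---|---|
| 5 | 15 | 15 to 20 | 0 |
| 6 | 14 | 14 to 20 | 1 |
| 7 | 13 | 13 to 20 | 2 |
| 8 | 12 | 12 to 20 | 3 |

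With *w* = 6 and half recorded, the row reads 14 + 3 = 17.

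**5. Chance that the row reaches 15 when the true count does not.** Let true completers X ~ Binomial(20, *p*), and withdrawals with a recorded EoT Visit Y ~ Binomial(20 − X, *q*), both *p* and *q* assumed. P(X < 15 and X + Y ≥ 15) is:

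| *p* | P(X < 15) | *q* = 0 | *q* = 0.25 | *q* = 0.5 | *q* = 1 |
|---|---|---|---|---|---|
| 0.75 | 0.383 | 0.00 | 0.23 | 0.35 | 0.38 |
| 0.80 | 0.196 | 0.00 | 0.13 | 0.19 | 0.20 |
| 0.90 | 0.011 | 0.00 | 0.01 | 0.01 | 0.01 |

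These probabilities describe this row only, not the disposition table as a whole.

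**6. Which duration rule would work?**
- The EoT Visit is planned for Day 361 with a window of ± 4 days, so the earliest on-schedule visit is 361 − 4 = Day 357 and the latest is Day 365.
- With the SAP's 30.4375-day month, 361 / 30.4375 = 11.86 and 365 / 30.4375 = 11.99. A threshold of 12 such months would exclude every on-schedule completer.
- The Table 3 reset is also unsuitable here. A Q1M subject who misses only the Month 11 dose has a last dose at Month 10 (Day 301), so the end date becomes 301 + 30 = Day 331. That subject would fail a 357-day rule despite attending on Day 361.

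**The case against.** **The correct information sits beside the row.** The same table reports treatment completers from a direct eCRF question, study completers, and early treatment and study discontinuations with reasons. The SAP 8.1 note says that subjects who stop treatment but stay in the study are reported as treatment discontinuations. The disposition listing gives first and last dose dates and the EoT Visit date. With 6 early withdrawals, the treatment-completer row would read 14 if the eCRF question is answered correctly. This stands, and it limits the harm.

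**The wording may mean the Month 12 occurrence only.** The schedules place the EoT Visit at Month 12, and Table 3 ties it to Day 361. If the eCRF records withdrawal assessments under another visit, the first route closes. The eCRF is not available, so this cannot be settled. The second route stays open on either reading.

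**Stronger readings that the documents do not support.** A reader might infer that the trial could be reported as having reached its 15-completer target when it had not. Neither document names this row as the measure of that target, no decision rule depends on it, and the neighbouring rows would contradict an inflated count. A reader might also infer that every early withdrawal will be counted. Protocol 7.2 asks for the assessments only where possible, and how they are recorded is unknown.

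**Conclusion.** The point holds as a defect in one derivation. The SAP 8.1 row can include subjects without 12 months of treatment, contrary to Protocol 4.5 and to the capped Treatment Period in Table 3. The error can only push the row upward, by as many subjects as stopped early and have the visit recorded. In the illustration of 20 treated and 6 early withdrawals, that is 0 to 6 subjects on a true 14. The actual frequency is unknown, and the illustration rests on assumed withdrawal numbers and recording practice.

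No endpoint, analysis set or test uses the count, and an inflated value could be found from the same table and listing. It is therefore a minor to moderate correction, not a must-fix. It goes beyond missing detail, because the stated rule can give a wrong number.

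**What to change.** Redefine the row in SAP 8.1 so that a subject counts only if both conditions hold:

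1. The eCRF question on completing the treatment period is answered Yes.
2. The actual EoT Visit date, without the Table 3 reset, falls on or after study Day 357.

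The first condition is what removes the off-drug attendee, so it relies on sites answering that question correctly. The second removes the early withdrawal. State the threshold in study days, not in 30.4375-day months. Add a sentence saying that this row is the one compared with the target of at least 15 subjects completing 12 months of treatment.

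The cost is one derived flag, an edit to the SAP text and a possibly lower reported count. No data collection changes.

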8.2 Protocol Deviations

A protocol deviation occurs when an investigator site, or study subject, does not adhere to protocol-stipulated requirements. Deviations will be assessed by CSL as they are reported and evaluated periodically during study conduct. All identified protocol deviations throughout the study will be listed prior to DBL and will be classified as minor or major by CSL. Major protocol deviations are defined as deviations that could have a significant effect on the subject's safety, rights, or welfare and/or on the integrity of the study data. All protocol deviations will be listed.

The protocol deviations' classification into minor and major will be reassessed under statistical considerations. Under statistical considerations, protocol deviations leading to exclusion from an analysis set will be considered major. Protocol deviations not leading to exclusion from an analysis set will be considered minor. The classification of protocol deviations under statistical considerations, the subject's assignment to analysis sets, and the occurrence of intercurrent events (ICEs) will be discussed in detail during the PARM based on by-subject listings provided for the PARM. The decisions made during the PARM will be documented in the pre-DBL Planned Analysis Review Report prior to DBL for final analysis. After DBL, the PARM listings will be re-run on database locked data, and it will be checked/confirmed that no changes which may have an impact on the assignment of subjects to analysis sets or ICEs occurred. The final assignment of subjects to analysis sets will be documented in the post-DBL Planned Analysis Review Report.

Table 4 **Potential Protocol Deviations and/or Reasons for Exclusion From Analysis Sets**

Potential Protocol Deviations/Reasons for Exclusion	Potential Exclusion From Analysis Set
Subject did not provide informed consent and/or informed consent date missing	Screened, Enrolled, Safety, PP, PK, PD
Subject enrolled but not treated with IP	Safety, PP, PK, PD
Subject treated but with wrong dosing regimen	PP
Subject treated but does not have at least one measurable PK concentration after IP administration	PK
Subject treated but does not have at least one PD measurement	PD
Subject violated inclusion and/or exclusion criteria	Enrolled, PP, (Safety, PK, PD)
Subject treated but compliance outside 80-120%	PP, (PK, PD)
Subject treated but received prohibited concomitant medication	PP, (PK, PD)

Prior to the PARM, a list of concomitant medications used in the study will be provided to CSL as an Excel file in the same format as the corresponding listing of concomitant medications in the TLF shells. This Excel file will be reviewed by CSL and concomitant medication potentially interfering with the PK/PD analysis or with the efficacy analysis will be flagged. It will be discussed if subjects with such a concomitant medication flagged will be entirely excluded from the respective analysis set, if data after a specific time point will be excluded, or if the subject and data will not be excluded at all.

The following by-subject listings will be provided using the Screened Analysis Set (see [Section 5.1](#)):

- protocol deviations related to inclusion and exclusion criteria,
- protocol deviations leading to exclusion from any analysis set,
- other protocol deviations,

For the PARM, the following by-subject listings will be provided in addition based on the Enrolled Analysis Set:

- concomitant medications,
- study drug exposure,
- compliance,
- adverse events.

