#### **9.3.3. Safety Analysis Set**

The Safety Analysis Set consists of all subjects in the Enrolled Analysis Set who received at least 1 dose of investigational product. The Safety Analysis Set will be analyzed using the treatment that the subject actually received.

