5.2 Enrolled Analysis Set

The Enrolled Analysis Set consists of all subjects in the Screened Analysis Set who were enrolled into the study. Subjects are considered "enrolled" in the study when they, or their legally authorized representative, has agreed to participate in the study after completing the informed consent process and Screening. Potential subjects who are screened to determine their eligibility but fail Screening or do not meet all the eligibility criteria, are not considered enrolled.

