5.3 Safety Analysis Set

The Safety Analysis Set comprises all subjects in the Enrolled Analysis Set who received at least 1 dose of investigational product (IP). The Safety Analysis Set will be analyzed using the treatment that the subject actually received.

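### SAP Table 4 conflicts with the nested analysis-set definitions and permits, without requiring, removal of a dosed child from the primary safety and PK analyses.

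*SAP*

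**What the plan says.** **Table 4 (SAP 8.2).** The column is headed "Potential Exclusion From Analysis Set". For the row "Subject violated inclusion and/or exclusion criteria" the entry reads "Enrolled, PP, (Safety, PK, PD", with the last three sets in parentheses. The parentheses are not explained.

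**Enrolled (SAP 5.2; protocol synopsis, Number of Subjects).** A subject becomes enrolled on agreeing to take part after consent and Screening are complete. The next sentence says that potential subjects who are screened but "fail Screening or do not meet all the eligibility criteria, are not considered enrolled".

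**Safety (protocol 9.3.3; same rule in SAP 5.3).** The set is "all subjects in the Enrolled Analysis Set who received at least 1 dose of investigational product".

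**PK and PD (SAP 5.5 and 5.6; protocol 9.3.5 and 9.3.6).** Both are drawn from the Safety set, given evaluable data.

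**Use of the sets.** The primary TEAE rate per subject year uses Safety (SAP 10.2.2). The primary PK parameters use PK (SAP 11). Secondary efficacy uses Enrolled (SAP 9.2.1).

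**Who decides.** SAP 8.2 says that "the subject's assignment to analysis sets, and the occurrence of intercurrent events (ICEs) will be discussed in detail during the PARM". It adds: "For the PARM, the following by-subject listings will be provided in addition based on the Enrolled Analysis Set". Those extra listings cover concomitant medication, exposure, compliance and adverse events.

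**The concern.** A safety population should hold everyone who was exposed. Here its membership depends on Enrolled, and Table 4 names an eligibility violation as a ground for leaving Enrolled. Eligibility in this trial rests partly on records that can be corrected after dosing: the attack count before Screening, the C1-INH and C4 results, and the time off prior prophylaxis (protocol 5.1 and 5.2). A child could be injected, followed and only later found ineligible.

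Both primary endpoints would be affected: the TEAE rate through Safety, and the steady-state PK parameters through PK. The secondary efficacy set would shrink by the same route. The study is open-label and adverse events are on the table when sets are assigned, so without a fixed rule the decision can be made, or can appear to have been made, with knowledge of the child's outcome.

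**Working it through.** The documents contain no power or sample-size calculation to reproduce. The target of about 20 was agreed with health authorities. The check is mainly one of logic.

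**Step 1: the nesting.** For a child who received a dose and has evaluable PK and PD data:

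- Safety = Enrolled and dosed
- PK = Safety and at least one quantifiable concentration
- PD = Safety and at least one PD measurement

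| Enrolled | Safety | PK | PD |
|---|---|---|---|
| yes | yes | yes | yes |
| no | no | no | no |

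The outcome that Table 4 seems to offer, out of Enrolled but kept in Safety, PK or PD, does not exist under these definitions.

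**Step 2: the same parentheses in other rows.** The rows for compliance outside 80-120% and for prohibited medication list Per-protocol outright and PK and PD in parentheses. There an optional reading works, because PK and PD are not subsets of Per-protocol. In the eligibility row it fails, because the set named outright is the parent of the sets in parentheses.

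**Step 3: the listings.** The extra PARM listings are based on Enrolled. A child already flagged as not enrolled would be missing from the adverse event and exposure listings used at the meeting that decides the matter.

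**Step 4: size, as an illustration.** The documents do not say how many dosed children might be ineligible. Assume 20 dosed, one of them later found ineligible, and one year of exposure each.

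- Share of the set: 1/20 = 5.0%, or 1/15 = 6.7% of the minimum number of completers. The split between regimens is not stated. If a regimen held 5 to 10 children, one child would be 20% to 10% of it.
- A sole event in that child: 1/20 = 5.0% (95% Wilson interval 0.9% to 23.6%) becomes 0/19 = 0% (0.0% to 16.8%).
- Primary summary, TEAEs per subject year: if the other 19 children have b events each and this child has m, the rate is (19b + m)/20 with the child and b without.

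| b | m | With child | Without | Change on removal |
|---|---|---|---|---|
| 2 | 0 | 38/20 = 1.90 | 2.00 | +5.3% |
| 2 | 2 | 40/20 = 2.00 | 2.00 | 0% |
| 2 | 5 | 43/20 = 2.15 | 2.00 | -7.0% |
| 2 | 10 | 48/20 = 2.40 | 2.00 | -16.7% |
| 1 | 10 | 29/20 = 1.45 | 1.00 | -31.0% |
| 4 | 10 | 86/20 = 4.30 | 4.00 | -7.0% |

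The change can go either way and can be nil. It is large only when the removed child's event count differs greatly from the others'.

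**The case against.** **Removal is not automatic.** A reader might infer that any dosed child later found ineligible drops out of the safety analysis. The documents do not say so. The Table 4 exclusions are potential, the parentheses suggest that removal from Safety was meant to be discretionary, and each case goes to the PARM before database lock. This stands, and the point is limited to what the plan permits.

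**The Enrolled definition mostly describes screen failures.** The excluding sentence in SAP 5.2 is about potential subjects being screened, and the sentence before it makes a child enrolled once consent and Screening are complete. Eligibility is also confirmed on Day 1, before dosing, and waivers are prohibited (protocol 5). So SAP 5.2 alone does not clearly un-enrol a dosed child. This stands too, although SAP 8.1 glosses enrolled as eligible to enter the study, which leans the other way. The route out rests mainly on the Table 4 row.

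**The treatment-policy wording is not contradicted.** A reader might infer that removal breaches the estimand's promise to use all observed values. That promise covers the listed intercurrent events: on-demand medication, prohibited medication, and adherence or discontinuation. An eligibility violation is not among them. The estimand population is itself described by the eligibility criteria together with at least one dose (SAP 10.2.1), so excluding an ineligible child arguably fits it.

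**Removal would be visible.** Eligibility deviations are listed on the Screened set, set assignment is listed with reasons for exclusion, and disposition counts everyone who received any dose. All adverse events are also to be listed (SAP 10.2), although SAP 10 bases safety analyses on the Safety set, so that protection is not watertight. Visibility limits the harm but does not return the child to the primary rate.

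**Conclusion.** The plan contradicts itself and should be corrected before database lock. Table 4 treats Safety, PK and PD as optional exclusions under a parent exclusion that leaves no option. As written, a dosed child can be taken out of both primary analyses by a case-by-case decision, in an open-label study, with adverse events available and no stated rule.

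The logic depends on no assumption. The size does: with one such child among 20 and one year of exposure each, a sole event goes from 1/20 to 0/19, and the TEAE rate moves by +5.3% to -31.0% over the scenarios shown. The documents neither say that any such child exists nor suggest that sets would be assigned to suit the results. The defect is that the plan leaves the possibility open.

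**What to change.** 1. **SAP 5.3 and protocol 9.3.3.** Define the Safety Analysis Set as every subject who received at least one dose of CSL312, regardless of eligibility, and not by way of the Enrolled set.
2. **SAP 5.2 and protocol synopsis.** State that an eligibility violation found after enrolment does not reverse enrolment. The PARM listings, which use Enrolled, would then include the child without further change. The gloss on enrolled in SAP 8.1 should follow.
3. **SAP Table 4.** Limit the eligibility row to Per-protocol, and add a footnote saying what the parentheses mean in the rows that keep them.
4. **Estimand population (protocol synopsis, protocol 9.4.3.1, SAP 10.2.1).** Align the reference to eligibility criteria with the revised Safety set. Otherwise the new set and the estimand will disagree.

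The PK and PD definitions need no change, since they already follow from Safety plus evaluable data.

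The cost is wording only, with no new data or procedures. It is more than a one-line clarification, because it touches the protocol synopsis in two places, protocol 9.3.3 and 9.4.3.1, and several SAP sections.
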